CRF	Case Report Form
CRC	Clinical Research Center
CRO	Contract Research Organization
DBP	Diastolic Blood Pressure
DMSO	Dimethyl sulfoxide
ECG	Electrocardiogram
GCP	Good Clinical Practice
HbA1c	Glycated hemoglobin
HBV	Hepatitis B virus
HCV	Hepatitis C virus
HIV	Human immunodeficiency virus
HR	Heart Rate
ICF	Informed Consent Form
IB	Investigator's Brochure
ICH	International Conference on Harmonization
IEC	Independent Ethics Committee
Im	Intramuscular

IRB	Institutional Review Board
IUD	Intra-uterine device
Iv	Intravenous
Kg	Kilogram
L	Liters
LSLV	Last Subject Last Visit
MedDRA	Medical Dictionary for Regulatory Activities
Mg	Milligram
min	Minute
mmHg	Millimeters Mercury
mM	Millimoles per Liter
NOAEL	No Observed Adverse Effect Level
PG	Plasma Glucose
PD	Pharmacodynamics
PK	Pharmacokinetic
RBC	Red blood cells
rDNA	Recombinant
RLD	Reference Listed Drug
SAE	Serious Adverse Event
SBP	Systolic Blood Pressure
Sc	Subcutaneous
THC	Tetrahydrocannabinol
Tmax	Time to Maximum Plasma Concentration
T1D	Type 1 Diabetes Mellitus
ULN	Upper Limit of Normal

VAS	Visual Analog Scale
WHO	World Health Organization
YSI	Yellow Springs Instrument

1 OVERVIEW

1.1 INTRODUCTION

This documentation describes the planned data analyses for clinical trial XSGP-303 sponsored by Xeris Pharmaceuticals, Inc.

1.2 OBJECTIVES

1.2.1 Primary Objective

The primary objective of this study is to demonstrate the efficacy (return to plasma glucose >70.0 mg/dL) of G-Pen 1 mg (test) to be non-inferior to Lilly Glucagon 1 mg (reference), in T1D subjects in a state of insulin-induced hypoglycemia. This will be assessed by the comparison of failure rates of plasma glucose to have a measured value > 70.0 mg/dL within 30 minutes of administration of glucagon.

1.2.2 Secondary Objectives

The secondary objectives of this study are:

- To demonstrate the efficacy (either return to plasma glucose >70.0 mg/dL or an increase in plasma glucose ≥ 20 mg/dL within 30 minutes post study drug injection) of G-Pen 1 mg (test) to be non-inferior to Lilly Glucagon 1 mg (reference), in T1D subjects in a state of insulin-induced hypoglycemia.
- To demonstrate the efficacy (return to plasma glucose >70.0 mg/dL or alleviation of all neuroglycopenic symptoms at 30 minutes post study drug injection) of G-Pen 1 mg (test) to be non-inferior to Lilly Glucagon 1 mg (reference), in T1D subjects in a state of insulin-induced hypoglycemia.
- To compare the pharmacodynamics characteristics of G-Pen 1 mg (test) versus Lilly Glucagon 1 mg (reference) in T1D subjects who are in a state of insulin-induced hypoglycemia.
- To compare G-Pen (test) and Lilly Glucagon (reference) with regards to hypoglycemia symptom relief.
- To compare G-Pen (test) and Lilly Glucagon (reference) with regards to the preparation time required to inject to the abdomen from a decision to treat.
- To compare the safety and tolerability of G-Pen 1 mg (test) versus Lilly Glucagon 1 mg (reference) in T1D subjects who are in a state of insulin-induced hypoglycemia.

1.3 ANALYSIS SOFTWARE

SAS 9.1.3 or newer (Windows)

1.4 MODIFICATIONS FROM THE STATISTICAL SECTION IN THE PROTOCOL

None

2 INVESTIGATIONAL PLAN

2.1 STUDY DESIGN AND RANDOMIZATION

2.1.1 Study Design

This is a non-inferiority, multi-centered, randomized, controlled, single-blind, two-way crossover efficacy and safety in-patient study in subjects with Type 1 diabetes mellitus (T1D).

Table 2-1: Randomized treatment sequence

Group	Dose 1	Dose 2
1	G-Pen™ 1 mg	Lilly 1 mg
2	Lilly 1 mg	G-Pen™ 1 mg

The procedure consists of:

1. Inducing hypoglycemia by IV administration of regular insulin diluted in normal saline until the subjects reach a verified stable hypoglycemic state.
2. Treating subcutaneously with either 1 mg Lilly Glucagon or 1 mg G-Pen™ (glucagon injection).

Blood glucose levels will be monitored for up to 180 minutes post-dosing. Subjects will also complete a questionnaire about symptoms of hypoglycemia during the hypoglycemia induction phase and for up to 180 minutes after treatment with glucagon.

The specific hypoglycemia induction procedures and justification, and rules for interruption and termination of dosing are listed in the protocol.

2.1.2 Sample Size

For the primary objective, a failure is recorded if the subject's plasma glucose fails to rise above 70.0 mg/dL within 30 minutes of administration of the dose of glucagon. Using this criterion, a sample size of 85 randomized subjects yields probabilities of G-Pen acceptance of 88% if the population failure rate differences of G-Pen and control are within 2%, and the rate of missing observations is within 5%.

Subjects will be recruited at approximately 6 clinical sites with a goal of no single center accounting for > 20% of the total sample.

2.1.3 Randomization

Randomization will be carried out via the Vision™ electronic data capture (EDC) system, version 9.3. Subjects meeting all eligibility criteria and achieving a baseline euglycemic steady state at the first treatment visit as described in the protocol, completing the baseline will be randomized 1:1 by site in simple blocks to receive G-Pen™ glucagon or Lilly glucagon injection at the first treatment visit.

2.1.4 Unblinding

This is a single-blind study. Only the subjects are blinded for treatment. The investigator and clinical staff will be aware of the treatment. Thus, there is no unbinding needed.

3 STATISTICAL AND ANALYTICAL PROCEDURES

3.1 ANALYSIS POPULATIONS

3.1.1 Intent-to-Treat (ITT) population

The intent-to treat (ITT) population is defined as all subjects randomized. A subject's randomized treatment will be used for analysis regardless of the actual treatment received.

3.1.2 Per-protocol (PP) Population

The Per-protocol (PP) population is defined as all randomized patients who, during both study periods, successfully complete the insulin induction procedure, fulfill the criteria for having achieved a hypoglycemic steady state, and successfully receive a dose of both study drugs (G-Pen followed by Lilly Glucagon, or Lilly Glucagon followed by G-Pen).

3.1.3 Safety Population

The safety population is defined as all subjects randomized. However, the actual treatment received will be used for analysis. Safety population will be used for all safety analyses (section 3.3.4).

3.2 ANALYSIS VARIABLES

3.2.1 Handling of Hypoglycemia Induction Procedure Data

Specific rules were applied to creation of the analysis dataset for the hypoglycemia induction procedure data (Appendix 3).

3.2.2 General guideline for define the protocol time

Protocol time is needed to find the 30-minute glucose value as well as to generate some of the glucose or hypoglycemia score curves.

Protocol time will be developed based on the following procedures:

- Protocol time zero will be based on either receiving glucagon or decision to dose:

- Receiving glucagon: T0 = actual time stamp of glucagon injection
- Decision to dose: T0 = actual time stamp when dose decision is made
- Subsequent protocol times are calculated by the following minutes plus T0:
 - 5, 10,15,20,25,30,35,40,45,50,55,60,65,70,75,80,85,90
 - 120,150,180
- For any continuous (number) variable, the value at the protocol time will be determined by linear interpolation between the two adjacent time points.
- For any categorical (text) variable, the value at the protocol time will be determined using the nearest value:
 - Protocol time 5 – 85 : -2 minute to +3 minute
 - Protocol time 90: -2 minute to 15 minute
 - Protocol time 120, 150, 180: -15 minute to +15 minute
 - If multiple values are attributed to a single protocol time, then the last value will be used

Many analyses will be done using both the protocol time based on receiving glucagon and the one based on decision to dose. These analyses will be noted in each of the corresponding sections.

3.2.3 For categorical variables, the last entered value will be used

3.2.4 Demographics

3.2.4.1 Age

Age in years will be calculated as follows:

$$\text{Age} = \frac{(\text{date of screening} - \text{Date of birth})}{365.24}$$

3.2.4.2 Gender, Race and Ethnicity

These variables will be imported directly from the EDC. The Race and Ethnicity category will be combined (i.e. Whites, Hispanics, and African-Americans) for subgroup analysis.

3.2.4.3 Medical History

Medical History data will be imported directly from the EDC. No coding is planned.

3.2.4.4 Prior and Concomitant Medications

Medications will be imported directly from the EDC. It will be coded with the latest version of the WHO drug dictionary.

- If a medication cannot be found in WHO dictionary, it will be coded as “Who Code Not Defined”

3.2.5 Efficacy Variables

The following efficacy variables will be considered in the efficacy analyses.

3.2.5.1 Primary Endpoint: Sample Mean of Failure Scores

The primary endpoint of the study is the failure score, where a failure is defined as the event when plasma glucose of a subject remains ≤ 70 mg/dL throughout the 0-30-minute period from the administration of study drug. The 30 minutes referenced in this section will be based on the protocol time. If the value to be analyzed was not collected at exactly 30 minutes, the value will be determined by linear interpolation between the two adjacent time points as mentioned in section 3.2.1.

The following scoring system will be applied to determine the failure score.

- If a G-Pen failure is observed then the treatment failure score = 1; similarly the control failure score = 1 if a control failure is observed.
- If the G-Pen treatment outcome is missing then the treatment failure score = 0.2. A missing control outcome yields a control failure score = 0.1. Note that for PP population, this will not apply since PP subjects always have both treatments outcomes.
- An observed successful plasma glucose rising above 70 mg/dL within 30 minutes yields a failure score = 0, for either treatment.

The following variables will be derived from the failure score.

- For each subject, derived score is the G-Pen minus Lilly failure score (Dht).
- Then from an analysis population, the sample Mean (Dht) and Standard Error SE (Dht) ($SE = \text{Standard Deviation of Dht} / \text{square root of N}$) will be obtained.

Secondarily, this will be repeated with success/failure evaluated at a time point of 30 minutes from a decision to dose.

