3.2.5.2 Secondary Endpoints

3.2.5.2.1 Binary Responses

The following secondary response endpoints will be assessed. Mean (Dht) and SE (Dht) corresponding to these conditions will be evaluated based on the same system defined in section 3.2.5.1. The 30 minutes reference in this section will be the protocol time.

1. Return of plasma glucose to > 70 mg/dL or neuroglycopenic symptomatic relief within 30 minutes after receiving glucagon. The Baseline Glucose will be the last glucose measurement prior to time 0.
2. Return of plasma glucose to > 70 mg/dL or an increase in plasma glucose by ≥ 20 mg/dL within 30 minutes after receiving glucagon. The Baseline Glucose will be the last glucose measurement prior to time 0.
3. Increase in plasma glucose by ≥ 20.0 mg/dL within 30 minutes after receiving glucagon. The Baseline Glucose will be the last glucose measurement prior to time 0.
4. Neuroglycopenic symptomatic relief within 30 minutes after receiving glucagon.

Secondarily, this will be repeated with success/failure evaluated at a time point of 30 minutes from a decision to dose.

3.2.5.2.2 Number of subjects having glucose >70 mg/dL within 30 minutes of receiving glucagon

This will be the raw count of subjects at protocol time points: 5, 10, 15, 20, 25, and 30 minutes.

This analysis will be done both based on time from receiving glucagon and from a decision to dose.

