3.2.5.2.3 Pharmacodynamics (PD) Parameters

The PD endpoints will be derived from the individual glucose profiles. The Baseline Glucose will be the last glucose measurement prior to time 0.

Actual Time will be used to the calculation of the following variables.

If insulin starts after receiving glucagon, the glucose values post insulin start will be censored out and considered as missing.

- Cmax : Maximum concentration of Glucose
- TMax : Time (in mins) when Glucose CMax is reached
- AUC₀₋₃₀: Area under the curve of Glucose from 0 to 30 minutes

- AUC₀₋₃₀ of Glucose will be calculated as the sum of areas of trapezoids, which are composed of adjacent Glucose values. The following rules will be considered:
 - If there are missing data points before the last observed value, they will be imputed as described in section 3.2.1
 - If there are missing data points after the last observed value, they will not be extrapolated and the AUC will be treated as undefined.
- AUC₀₋₁₈₀: Area under the curve of Glucose from 0 to 180 minutes
 - AUC₀₋₁₈₀ of Glucose will be calculated as the sum of areas of trapezoids, which are composed of adjacent Glucose values. The following rules will be considered:
 - If there are missing data points before the last observed value, they will be imputed as described in section 3.2.1.
 - If there are missing data points after the last observed value, they will not be extrapolated and the AUC will be treated as undefined.
- Time for plasma glucose to reach >70.0 mg/dL from receiving of glucagon.
 - The time stamp for 70.0 mg/dL will be imputed using linear interpolation between the two adjacent time points
- Time for plasma glucose to increase by at least 20 mg/dL from receiving of glucagon.
 - The time stamp for 20 mg/dL increase will be imputed using linear interpolation between the two adjacent time points

These PD parameters will be done based on both receiving glucagon and decision to dose.

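### The failure score has no rule for exogenous glucose or for stopping because of non-response, so if either occurs by about 30 minutes a non-responder can score 0, or 0.2/0.1 in ITT, instead of 1

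*SAP*

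**What the plan says.** SAP 3.2.5.1 assigns 1 to a subject whose glucose stays at or below 70 mg/dL for the whole 30 minutes after dosing. Success is defined by the reading alone: "An observed successful plasma glucose rising above 70 mg/dL within 30 minutes yields a failure score = 0, for either treatment".

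Missing outcomes get a fixed score with no reference to cause: "If the G-Pen treatment outcome is missing then the treatment failure score = 0.2", and 0.1 for control. For PP the SAP adds: "Note that for PP population, this will not apply since PP subjects always have both treatments outcomes".

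If no sample falls at exactly 30 minutes, "the value will be determined by linear interpolation between the two adjacent time points as mentioned in section 3.2.1". The general rule, which actually stands in 3.2.2, is the same: "For any continuous (number) variable, the value at the protocol time will be determined by linear interpolation between the two adjacent time points".

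Section 3.2.5.2.1 carries the scoring over to the binary secondary endpoints, which "corresponding to these conditions will be evaluated based on the same system defined in section 3.2.5.1".

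The only rule on glucose readings affected by a treatment after dosing is in 3.2.5.2.3 and concerns insulin and the PD parameters: "If insulin starts after receiving glucagon, the glucose values post insulin start will be censored out and considered as missing". The PP definition (3.1.2), the major violations (4.3) and the missing-data section (4.1) do not mention exogenous glucose or carbohydrate.

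**The concern.** The endpoint is meant to count subjects whom glucagon did not bring above 70 mg/dL. Those same subjects are the ones most likely to be given glucose or taken off observation. The scoring does not ask why a reading rose or why an outcome is missing, so three routes lead away from a score of 1:

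- **Treatment inside the window.** Glucose is given before 30 minutes and a later reading exceeds 70 mg/dL. Score 0, in ITT and PP.
- **Treatment at about 30 minutes.** The sample after 30 minutes is taken after treatment, and interpolation pulls the 30-minute value above 70 mg/dL. Score 0, in ITT and PP.
- **Early stop.** Observation ends before 30 minutes for non-response and the outcome is classed as missing. Score 0.2 or 0.1, in ITT only.

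A hidden G-Pen failure favours non-inferiority; a hidden control failure works against it. Few failures are expected, so a single score can decide the primary result.

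**Working it through.** **Inputs.** N = 85 randomized (2.1.2). Accept if mean(D) + 2.8 SE ≤ 0.1, where D is the G-Pen minus control score and SE = SD/√N (3.2.5.1, 3.3.3.1). SD is taken with divisor n−1. Planned power is 88% for a difference within 2% and missingness within 5% (2.1.2).

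**Step 1: reproduce the plan's figure.** The SAP gives no absolute failure rates. Assuming 0% for control and 2% for G-Pen, simulation of the SAP's own scoring and rule (40,000 trials per case) gives power of 87.4% with 5% missing per treatment independently, and 89.7% with 5% of subjects missing one outcome. That agrees with 88%. At control rates of 0.5%, 1% and 2%, with the 2-point difference kept and 5% missing, power is about 81–83%, 73–76% and 59–60%. The 88% is not in dispute; it shows that the rule is being read as intended.

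**Step 2: the boundary.** Four G-Pen failures, no control failures, nothing missing:

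- All four scored 1: mean = 4/85 = 0.0471, SE = 0.0231, sum 0.1118. Not accepted.
- One scored 0.2: mean = 3.2/85 = 0.0376, SE = 0.0202, sum 0.0943. Accepted.
- One scored 0: mean = 3/85 = 0.0353, SE = 0.0201, sum 0.0917. Accepted.

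In PP with an assumed 81 subjects, only the 0 route applies: 0.1172 becomes 0.0962.

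**Step 3: sensitivity to other missing data.** 5% of 85 is about 4.

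| Other missing outcomes | Scored 1 | One scored 0.2 | One scored 0 |
|---|---|---|---|
| None | 0.1118 | 0.0943 | 0.0917 |
| 4 per arm, different subjects | 0.1178 | 0.1006 | 0.0980 |
| 4 subjects missing both | 0.1165 | 0.0990 | 0.0965 |

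In the middle row the 0.2 route no longer changes the verdict.

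**Step 4: the other direction.** Four subjects fail on G-Pen only and three on control only: mean = 1/85, sum 0.0994, accepted. With one control failure scored 0.1 or 0, the sum is 0.1033 or 0.1044, not accepted.

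**Step 5: how likely is a changed verdict?** Let each subject fail on G-Pen with probability p, and let each failure independently be scored 0 with probability q (assumed). With no control failures and nothing missing, the verdict changes when at least 4 fail but at most 3 are scored 1:

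P = P[Bin(85, p(1−q)) ≤ 3] − P[Bin(85, p) ≤ 3]

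For p = 2% and q = 25% this is 0.9606 − 0.9088 = 0.052.

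| p | q = 5% | q = 10% | q = 25% |
|---|---|---|---|
| 1% | 0.002 | 0.003 | 0.007 |
| 2% | 0.012 | 0.024 | 0.052 |
| 3% | 0.027 | 0.054 | 0.126 |

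**Step 6: interpolation.** Assumed values: 60 mg/dL at 28 min, glucose given at 31 min, 90 mg/dL at 33 min. The 30-minute value is 60 + (30−28)/(33−28) × (90−60) = 72 mg/dL, a success produced by treatment after the window. With samples at 28 and 33 min, the later value must exceed 100, 85 or 77.5 if the earlier one is 50, 60 or 65; at 29 and 34 min it must exceed 150, 110 or 90.

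**The case against.** The strongest reply is that the problem may never arise. Treatment of persisting hypoglycemia is normally a protocol matter, the protocol is an appendix to this SAP, and two further appendices (induction data; populations and violations) may bear on it. That stands as a limit: the SAP shows a gap in a scoring rule and not an actual misclassification. It does not remove the point, because how such an outcome is scored is exactly what 3.2.5.1 sets out to fix.

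Four further points stand in part:

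- A reader might take the mention of interruption and termination in 2.1.1 as evidence that subjects can be stopped after glucagon. It is not: that sentence concerns induction and dosing.
- The 0.2/0.1 route requires that a stopped subject be classed as missing. The SAP does not say so, and such a subject could equally be called an observed failure.
- The interpolation route needs no sample at 30 minutes, treatment close to that time and a steep rise. It is an edge case.
- Scoring treatment as failure brings a decision by unblinded staff into a laboratory endpoint, and a slow responder treated early might have passed 70 mg/dL unaided. This is why the as-measured score should also be reported.

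A reader might also infer that the PD parameters need a matching rule. I do not propose one. The mixed model in 3.3.3.2.3 has no method for censored times. Under the existing AUC rule for data missing after the last observed value, "they will not be extrapolated and the AUC will be treated as undefined", so discarding values after treatment would remove the poorest responders selectively.

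**Conclusion.** The point holds in conditional form. The scoring rule as written would count a treated non-responder as a success, or a stopped one as a fraction of a failure, if such cases occur by about 30 minutes. At the boundary one subject reverses the verdict (0.1118 against 0.0917 or 0.0943, under the assumptions of Step 2). The overall chance is modest: 0.012 to 0.052 at a 2% G-Pen failure rate, with assumed mis-scoring of 5% to 25%.

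A reader might infer that the plan is biased in favour of G-Pen, or that failures will in fact be hidden. The SAP supports neither. The direction depends on the arm, and the frequency is not given. A treated subject whose values, including any interpolated one, stay at or below 70 mg/dL through 30 minutes already scores 1. The change is worth making because it is cheap and costs almost nothing if the cases never arise. Confidence is medium, since the protocol may already settle the matter.

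**What to change.** In 3.2.5.1 and 3.2.5.2.1, for either treatment:

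1. Score 1 if exogenous glucose or carbohydrate is given for hypoglycemia, or observation is stopped for persisting hypoglycemia, within the 30-minute window and before that endpoint's criterion is met.
2. Do not interpolate the 30-minute value across a treatment time; use the last value before treatment.
3. Keep 0.2/0.1 for missing outcomes unrelated to response.
4. Report the as-measured score (the current rule) as a sensitivity analysis, because staff know the treatment.

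If the protocol rules out treatment and stopping before 30 minutes, only item 2 is needed. This concerns scoring only; when subjects are treated stays as the protocol has it.

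Cost: a few sentences, one sensitivity table, and a dataset flag for the time of glucose or carbohydrate and the reason for stopping, if these are not already captured. The wording should be checked against the protocol's endpoint definition. No extra subjects are needed. Downsides: a slightly higher failure rate is possible in either arm, and a slow responder treated early counts as a failure.

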3.2.5.2 Secondary Endpoints

3.2.5.2.1 Binary Responses

The following secondary response endpoints will be assessed. Mean (Dht) and SE (Dht) corresponding to these conditions will be evaluated based on the same system defined in section 3.2.5.1. The 30 minutes reference in this section will be the protocol time.

1. Return of plasma glucose to > 70 mg/dL or neuroglycopenic symptomatic relief within 30 minutes after receiving glucagon. The Baseline Glucose will be the last glucose measurement prior to time 0.
2. Return of plasma glucose to > 70 mg/dL or an increase in plasma glucose by ≥ 20 mg/dL within 30 minutes after receiving glucagon. The Baseline Glucose will be the last glucose measurement prior to time 0.
3. Increase in plasma glucose by ≥ 20.0 mg/dL within 30 minutes after receiving glucagon. The Baseline Glucose will be the last glucose measurement prior to time 0.
4. Neuroglycopenic symptomatic relief within 30 minutes after receiving glucagon.

Secondarily, this will be repeated with success/failure evaluated at a time point of 30 minutes from a decision to dose.

3.2.5.2.2 Number of subjects having glucose >70 mg/dL within 30 minutes of receiving glucagon

This will be the raw count of subjects at protocol time points: 5, 10, 15, 20, 25, and 30 minutes.

This analysis will be done both based on time from receiving glucagon and from a decision to dose.

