3.2.5.2.5 Symptom relief

Symptom relief of hypoglycemia is defined as a return to a score (ANS, AAS and ATS) no more than one unit above baseline symptoms during the euglycemic baseline period, where the baseline symptom is the minimal values of score (ANS, AAS and ATS) prior to receiving glucagon (T0).

The time (min) to Symptom relief will be derived for analysis purpose. Actual Time will be used in calculation.

This parameter will be done based on both receiving glucagon and decision to dose.

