3.2.5.2.6 The time to the minimal score post dose

This will be calculated for sub-scales ANS, AAS and ATS as the difference (in mins) between the actual time when the minimal number is observed and the time of receiving glucagon. Actual Time will be used to the calculation of the following variables.

- Subjects who never develop symptoms will be assumed to have a value of 0.

This parameter will be analyzed both on time from receiving glucagon and from a decision to dose.

3.2.5.2.7 The time to first reporting of “no” for the global hypoglycemia question will be defined as below:

This will be calculated as the difference (in mins) between the actual time when the first “no” for “Overall Assessment of Hypoglycemia” is observed and the time receiving glucagon. Actual Time will be used to the calculation of the following variables.

- Subjects who never develop symptoms (never answers No) will be assumed to have a value of 0.
- In very rare cases, if subject answers Yes all the way to the last time point, the total time will be recorded. (And it will be analyzed based survival model.)

This parameter will be analyzed both on time from receiving glucagon and from a decision to dose.

3.2.5.2.8 The Glucagon Preparation Time:

Glucagon preparation time (min) is defined as the time between “decision to dose” and time of study drug administration to the abdomen. Actual Time will be used to calculate this variable.

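### The symptom composite tested for non-inferiority (SAP 3.2.5.2.1, response 1) is looser than the secondary objective it is meant to test (SAP 1.2.2)

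*SAP*

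**What the plan says.** - **Objective (SAP 1.2.2, second bullet):** non-inferiority of G-Pen on "return to plasma glucose >70.0 mg/dL or alleviation of all neuroglycopenic symptoms at 30 minutes post study drug injection".
- **Endpoint (SAP 3.2.5.2.1, response 1):** "Return of plasma glucose to > 70 mg/dL or neuroglycopenic symptomatic relief within 30 minutes after receiving glucagon". For scoring, the section refers only to 3.2.5.1, which deals with glucose. The only baseline it gives for response 1 is a glucose baseline. On timing it says "The 30 minutes reference in this section will be the protocol time", and it ends by stating that "this will be repeated with success/failure evaluated at a time point of 30 minutes from a decision to dose".
- **Test (SAP 3.3.3.2.1):** the primary endpoint's test is applied to each binary response. Under 3.3.3.1, non-inferiority is established if the mean score difference plus 2.8 SE is at most 0.1.
- **Relief (SAP 3.2.5.2.5):** the only definition in the document. Relief is "defined as a return to a score (ANS, AAS and ATS) no more than one unit above baseline symptoms during the euglycemic baseline period", and the section continues "where the baseline symptom is the minimal values of score (ANS, AAS and ATS) prior to receiving glucagon (T0". A separate paragraph adds: "The time (min) to Symptom relief will be derived for analysis purpose. Actual Time will be used in calculation".
- **Scores (SAP 3.2.5.2.4):** ANS is the mean of dizziness, blurred vision, difficulty in thinking and faintness, each scored 1 to 6.

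**The concern.** Two elements change between the objective and the endpoint. The requirement that *all* neuroglycopenic symptoms be alleviated disappears, and *at* 30 minutes becomes *within* 30 minutes. This does not look like uniform shorthand, because the objective listed just before it in 1.2.2 does use *within*.

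Response 1 carries a formal non-inferiority test, so a pass would be reported as meeting the stated objective although the rule tested was weaker. The missing reference also leaves the programmer to choose the score, threshold and symptom baseline. Only the subjects are blinded (SAP 2.1.4), so a choice made after the data are in would be made with treatment known.

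**Working it through.** No planned figure exists for response 1. The check is a comparison of texts followed by arithmetic.

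**1. Side by side**

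| Element | Objective (1.2.2) | Response 1 (3.2.5.2.1) | Relief rule (3.2.5.2.5) |
|---|---|---|---|
| Content | all neuroglycopenic symptoms alleviated | relief, not defined there | mean score ≤ baseline + 1 |
| Time | at 30 min | within 30 min, protocol time | time to relief, actual time |
| Symptom baseline | not stated | not stated | euglycemic period / minimum before T0 |

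**2. Content.** ANS = (sum of four items)/4. Assume a baseline of 1 on every item, so baseline ANS = 1.00. Relief is then ANS ≤ 2.00, that is, an item sum ≤ 8.
- 5,1,1,1: 8/4 = 2.00, relieved, with one item four units above baseline.
- 2,2,2,2: 8/4 = 2.00, relieved, with every item above baseline.
- Of 6^4 = 1,296 patterns, 70 have a sum ≤ 8. Only 1 of these has every item at baseline. Another 15 have no item above 2 (2^4 = 16, less that one). The other 70 − 16 = 54 leave at least one item two or more units above baseline.

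These are pattern counts. They show that the two rules differ, not how often patients would differ.

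**3. Timing.** A subject relieved at 15 minutes and symptomatic again at 30 is a success under *within* and not under *at*.

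**4. Which rule is looser.** Take the same baseline and the same 30-minute reading for both. If all four items are back to baseline at 30 minutes, their mean is at or below baseline, so the ANS rule is also met. The converse fails by steps 2 and 3. Response 1 therefore cannot have more failures than the objective's rule in either arm.

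**5. Where it can act.** Glucose above 70 mg/dL within 30 minutes is already a success. Only subject-periods with glucose ≤70 mg/dL can change class. The SAP gives no symptom rates, so their number cannot be calculated.

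**6. Direction.** Criterion: mean + 2.8 SE ≤ 0.1, with SE = SD/√N. Take N = 85 complete pairs and write counts as G-Pen-only/control-only failures. Totals use unrounded values.
- Reclassify one of each as a success, 4/1 to 3/0. The mean stays at 3/85 = 0.0353 and SE falls from 0.0262 to 0.0201. The criterion goes from 0.1086 (fail) to 0.0917 (pass).
- Reclassify one control-only failure, 4/3 to 4/2. From 0.0118 + 2.8 × 0.0313 = 0.0994 (pass) to 0.0235 + 2.8 × 0.0289 = 0.1044 (fail).

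The looser rule can move the result either way.

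**7. Scale under one planning assumption.** The 88% in SAP 2.1.2 belongs to the primary endpoint. Simulation gives 87.2% if control failure is 0% (assumed; not stated in the SAP), G-Pen failure 2% and missing outcomes 5% per treatment. On that assumption 85 × 0.02 = 1.7 G-Pen glucose failures are expected. With complete pairs, 1/0 gives 0.0447 and 2/0 gives 0.0698. Both pass even if no symptom relief is credited. Four or more G-Pen failures (4/0 = 0.1118, fail) have binomial probability of about 9%.

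**The case against.** The best defence is that this is a missing cross-reference. SAP 3.2.5.2.5 defines relief in a general sentence, and ANS is the neuroglycopenic score, so response 1 can naturally be read through it. The sentence on actual time stands apart and governs only the derived time variable. That is fair: a reader might infer that the SAP contains no definition of relief, and it does contain one. But applying it makes the conflict with 1.2.2 concrete, because a mean within one unit of baseline is not alleviation of all symptoms.

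A reader might also infer that 3.2.5.2.1 contradicts itself on timing, since the repeat is evaluated at a 30-minute time point. That sentence also closes 3.2.5.1, where the endpoint plainly covers the whole 0–30-minute period. Its evident purpose is to move time zero to the decision to dose, so it is no independent evidence.

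Two further points are ambiguities, not contradictions. The baseline wording in 3.2.5.2.5 can be read as naming two baselines, but its second clause can equally be taken as the operating rule. Subjects without symptoms have a convention in 3.2.5.2.6, "Subjects who never develop symptoms will be assumed to have a value of 0", but only for time to minimal score. Read literally, the relief rule makes them successes in response 1, while the word *return* could exclude them.

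Finally, the protocol is not shown and may define this endpoint, and SAP 1.4 declares no modifications from its statistical section. That is a reason to check the protocol before rewording. It does not remove the mismatch between two sections of the SAP.

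**Conclusion.** The point holds as a mismatch between a stated non-inferiority objective and the endpoint that tests it. With relief taken from 3.2.5.2.5 through ANS, and a common baseline and 30-minute reading, response 1 is the looser rule on both content and timing.

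The effect is confined to subject-periods with glucose ≤70 mg/dL in one secondary composite. Its frequency and direction are unknown. The primary endpoint and the sample size are not affected.

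Two stronger conclusions are tempting and not supported. One is that the wording favours G-Pen: the same rule applies to both drugs, and step 6 shows movement both ways. The other is that, because one subject can flip the test, the mismatch is large. Those pass/fail edges are a property of the 2.8 SE rule at N = 85 and would apply to any binary endpoint; they do not measure how many subjects this wording touches. Under the assumption in step 7, most trials would pass on either reading. This should be corrected, but it does not threaten the trial's main conclusion.

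**What to change.** Before database lock, check the protocol and reconcile SAP 1.2.2, 3.2.5.2.1 and 3.2.5.2.5:

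1. Make response 1 test the stated objective: all four neuroglycopenic items back to baseline at the 30-minute protocol time, with one named baseline. Leave the glucose part unchanged.
2. State how item scores are assigned to 30 minutes. SAP 3.2.2 interpolates numeric variables: an item at 2 at 25 minutes and 1 at 32 minutes becomes 2 − 5/7 = 1.29, above a baseline of 1. The nearest-value window (−2 to +3 minutes) would take the 1, but 3.2.2 gives that window to text variables, so using it here must be declared as a departure.
3. State how response 1 scores glucose ≤70 mg/dL with a missing item (observed failure at 1, or missing outcome at 0.2 or 0.1 under 3.2.5.1), and a period with no pre-dose symptoms.
4. Report the version with ANS within one unit of baseline, within 30 minutes, as a sensitivity analysis.
5. State which definition response 4 uses. It shares the phrase with response 1, and the two should not carry different meanings without a label.

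The cost is SAP wording and re-derivation from item scores already collected. Response 1 may show more failures and a larger SE, although its observed failures cannot exceed the glucose failures of the primary endpoint. A single time point is also more exposed to missing item scores, which is why item 3 is needed.
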